The total radiation whole body effective dose in this protocol will be less than 25 mSv; 14 mSv from HRCT scanning and 11 mSv from [F-18]FDG-PET/CT scans, including attenuation correction scans. In larger patients, a higher injected [F-18]FDG activity may be required but the total radiation exposure in these patients will not exceed 30 mSv. This amount of radiation is considered to be a moderate risk, category III (ICRP62) and is balanced against the substantial societal benefit gained from the trial. If patients have a historical [F-18]FDG-PET/CT scan that can be used as baseline scan, then only the follow up scan will be conducted as part of the clinical protocol.

As part of the spirometry assessment at Visits 101 and 107, a single dose of short-acting bronchodilators (SABA) salbutamol/albuterol will be administered. For more information please refer to product information (SmPC/USPI).

Women of child bearing potential should be informed that taking the study drug may involve unknown risks to the fetus if pregnancy were to occur during the study and agree that in order to participate in the study they must adhere to the contraception requirement for the duration of the study. If there is any question that the subject will not reliably comply, they should not be entered in the study.

There may be unknown risks of ACZ885 which may be serious and unforeseen.

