12. Inability or unwillingness to undergo repeated venipuncture (e.g., because of poor tolerability or lack of access to veins)
13. Donation or loss of blood (amount depending on age and weight, 10-20% or more of volume, within 8 weeks prior to first dosing, or longer if required by local regulation)
14. History of malignancy of any organ system (other than localized basal cell carcinoma of the skin), treated or untreated, within the past 5 years, regardless of whether there is evidence of local recurrence or metastases
15. Contraindications to FDG-PET scan investigations, such as severe claustrophobia or uncontrolled diabetes
16. Pregnant or nursing (lactating) women, where pregnancy is defined as the state of a female after conception and until the termination of gestation, confirmed by a positive hCG laboratory test

17. Women of child-bearing potential, defined as all women physiologically capable of becoming pregnant, unless they are using basic methods of contraception during dosing of investigational drug. ***Basic contraception methods include:***

- Total abstinence from heterosexual intercourse (when this is in line with the preferred and usual lifestyle of the subject). Periodic abstinence (e.g., calendar, ovulation, symptothermal, post-ovulation methods) and withdrawal are not acceptable methods of contraception
- Female sterilization (have had surgical bilateral oophorectomy with or without hysterectomy), total hysterectomy or tubal ligation at least 6 weeks before taking investigational drug. In case of oophorectomy alone, only when the reproductive status of the woman has been confirmed by follow up hormone level assessment
- Male sterilization (at least 6 months prior to screening). For female subjects on the study, the vasectomized male partner should be the sole partner for that subject.
- Barrier methods of contraception: condom or occlusive cap (diaphragm or cervical/vault caps). For UK: with spermicidal foam/gel/film/cream/vaginal suppository
- Use of oral, injected or implanted hormonal methods of contraception or other forms of hormonal contraception that have comparable efficacy (failure rate <1%), for example hormone vaginal ring or transdermal hormone contraception or placement of an intrauterine device (IUD) or intrauterine system (IUS)

In case of use of oral contraception women should be stable on the same pill for a minimum of 3 months before taking study drug

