## 8 Procedures and assessments

### 8.1 Assessment Schedule

	Epoch	Screening	Treatment							End of Study 	
	Study Phase	Screening	Treatment Period 								
		Visit Numbers 	1	101	102	103	104	105	106		
	Study Day(s)		40 to 0 -40 +0	1	29 -5 +5	57 -5 +5	85 -5 +5	113 -5 +5	141 -5 +5	169 -5 +5	224 -5 +5
Informed consent		S									
Inclusion / exclusion criteria		S	S								
Medical history/current medical conditions		X									
Demography		X									
Physical examination		S	S	S	S	S	S	S	S	S	
Smoking history		X									
Tuberculosis Blood Test		S									
Hepatitis and HIV Screen		S									
Urine drug screen and cotinine test		S									
Pregnancy test 		X	X							X	
Hematology		X	X	X	X	X	X	X	X	X	
Blood chemistry		X	X	X	X	X	X	X	X	X	
Urinalysis 		X	X	X	X	X	X	X	X	X	
Body height		X									
Body weight		X				X					
Body temperature		X	X	X	X	X	X	X	X	X	
Blood pressure 		X	X	X	X	X	X	X	X	X	
Spirometry		X		X	X	X	X	X		X	
Spirometry Reversibility Test			X 						X		
Diffusing Capacity (DLCO)				X	X	X	X	X	X	X	

 Visit structure given for internal programming purpose only

 A window of  $\pm 5$  days is allowed for the treatment visits, but the interval between 2 doses must be at least 21 days

 All patients who discontinue early must complete the EOS Visit. For those discontinuing after week 12, the volumetric and HRCT exam should also be included as assessed on a case-by-case basis by the Sponsor

 Limited to females of childbearing age. Serum testing is done at screening and urine test is done predose at Day 1 and at the EOS

 If the dipstick result is positive for protein, nitrite, leukocytes and/or blood, the sample should be sent for microscopic analysis of WBC, red blood cell count (RBC) and casts

 Vital signs taken after resting in a sitting position for at least 3 minutes

 For subjects at baseline who are unable to generate reproducible spirometry maneuvers, an additional 5 days beyond the 40 day screening window will be allowed for the subjects to return for repeat spirometry.

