### **8.6.6      Pregnancy and assessments of fertility**

All pre-menopausal women who are not surgically sterile will have pregnancy testing. See the [Assessment Schedule](#) for timing of the protocol required pregnancy testing; additional pregnancy testing may be performed to meet local requirements. A positive urine pregnancy test requires immediate interruption of study treatment until serum  $\beta$ -hCG is performed and found to be negative.

If additional pregnancy testing is needed per local requirements, those additional results will be kept as source documentation only.

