## **9.6      Pregnancy reporting**

To ensure patient safety, each pregnancy in a subject on study drug must be reported to Novartis within 24 hours of learning of its occurrence. The pregnancy should be followed up to determine outcome, including spontaneous or voluntary termination, details of the birth, and the presence or absence of any birth defects, congenital abnormalities, or maternal and/or newborn complications. The study drug must be discontinued, though the subject may stay in the study, if she wishes to do so. All assessments that are considered as a risk during pregnancy must not be performed. The subject may continue all other protocol assessments.

Pregnancy must be recorded on a Pharmacovigilance Pregnancy Form and reported by the investigator to the local Novartis Drug Safety and Epidemiology Department. Pregnancy follow-up should be recorded on the same form and should include an assessment of the possible relationship to the study treatments.

Any SAE experienced during pregnancy and unrelated to the pregnancy must be reported on an SAE Report Form.

Pregnancy outcomes should be collected for the female partners of any males who took study treatment in this study. Consent to report information regarding these pregnancy outcomes should be obtained from the mother.

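### No pregnancy test is scheduled between the Day 1 predose test and the end-of-study visit, so doses 2 to 6 and both on-treatment scan sessions go ahead without a new one

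*Protocol*

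**What the plan says.** The pregnancy-test row in Protocol 8.1 is marked at screening, Day 1 and the end-of-study (EOS) visit on Day 224. The cells for Days 29 to 169 are empty. Footnote 4 says the same in words: "Serum testing is done at screening and urine test is done predose at Day 1 and at the EOS". Footnote 3 adds that "All patients who discontinue early must complete the EOS Visit", so a patient who stops early has the last test sooner.

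Section 8.6.6 points to this schedule for the timing of required tests. Beyond that, "additional pregnancy testing may be performed to meet local requirements", with those results held in source documents only.

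Three rules apply once a pregnancy is found:

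- Section 8.6.6: "A positive urine pregnancy test requires immediate interruption of study treatment until serum" β-hCG comes back negative.
- Section 7.2: pregnancy is a ground for permanent discontinuation of study treatment.
- Section 9.6: "All assessments that are considered as a risk during pregnancy must not be performed".

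On prevention, Section 3.7 says that "taking the study drug may involve unknown risks to the fetus if pregnancy were to occur during the study", and that women must agree that "they must adhere to the contraception requirement for the duration of the study". Exclusion 17 (Section 4.2) bars women of child-bearing potential "unless they are using basic methods of contraception during dosing of investigational drug". The accepted methods include condoms and caps.

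Section 3.1 puts doses on Days 1, 29, 57, 85, 113 and 141, the second PET/CT at Week 12 and the second HRCT at the Week 24 visit. The low-dose volumetric CT accompanies the HRCT.

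**The concern.** The rules in Sections 7.2, 8.6.6 and 9.6 work only if a pregnancy is detected, and during treatment no scheduled test can detect one. The laboratory stopping criteria in Section 7.2 (neutropenia, thrombocytopenia) are treated differently: hematology is measured at every visit.

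Detection matters because exposure is hard to undo. Section 6.9 says no treatment reverses the drug's activity, although plasmapheresis may help, and Section 1.3.2 gives a half-life of 21 to 30 days. A repeat test cannot take back a dose already given, but it can stop the next dose and the next scan. The scans carry radiation whatever the drug's own fetal risk turns out to be.

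**Working it through.** The plan gives no figure to reproduce here. The check compares test days with dosing and scan days.

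**Inputs.** Test days: screening, Day 1 and Day 224, with ±5 days at EOS (Section 8.1). Doses of 300 mg: Days 1, 29, 57, 85, 113 and 141 (Section 3.1). Scans: Week 12, taken as Day 85, and Week 24, Day 169 (Section 3.1). Radiation: Sections 8.5.2.1 and 8.5.2.2.

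**Gap.** 224 − 1 = 223 days. With the EOS window, 219 − 1 = 218 to 229 − 1 = 228 days.

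**What falls inside it.**

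- Doses 2 to 6 come 28, 56, 84, 112 and 140 days after the Day 1 test. Together they are 5 × 300 = 1,500 mg.
- The PET/CT comes 85 − 1 = 84 days after that test, and the Week 24 CTs 169 − 1 = 168 days after it.
- The EOS test comes 224 − 141 = 83 days after the last dose and 224 − 169 = 55 days after the last scheduled scan. For a patient on schedule it can record a pregnancy but cannot prevent any planned exposure.

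**What an added visit test could stop.** This upper bound assumes the pregnancy would otherwise go unnoticed until EOS, the test is read before the dose, and the PET/CT is on or after the Day 85 visit or preceded by a test on the scan day. The milligram figures apply to the active arm.

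| First positive test | Doses stopped | mg | Scans stopped |
|---|---|---|---|
| Day 29 | 5 | 1,500 | PET/CT and CTs |
| Day 57 | 4 | 1,200 | PET/CT and CTs |
| Day 85 | 3 | 900 | PET/CT and CTs |
| Day 113 | 2 | 600 | CTs |
| Day 141 | 1 | 300 | CTs |
| Day 169 | 0 | 0 | CTs |

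If the pregnancy would be noticed by the next visit anyway, a test stops at most one dose (300 mg) plus any scan due at the visit of the positive test.

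**Radiation per session** (whole-body dose to the woman, not fetal dose). PET/CT: 4 + 1.5 = 5.5 mSv, or 16 / 2 = 8 mSv in large patients. CT pair: 14 / 2 = 7 mSv, assuming the total splits equally between the two sessions.

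**With tests added at Days 29 to 169.** There are six nominal gaps of 28 days, then 224 − 169 = 55 days. Visit windows make that last gap (224 − 5) − (169 + 5) = 45 to (224 + 5) − (169 − 5) = 65 days. No dose or scheduled scan falls in it.

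**The case against.** The strongest reply is that this is a choice, not an error. No two sections conflict, and no document sets a testing frequency that the schedule breaks. How often to test depends on reproductive toxicity, and Section 1.2.1 is redacted. The Site Operations Manual and the imaging manual are not available, and either could require a pre-scan check. That stands as a limit on what can be concluded, but Section 8.6.6 names the Assessment Schedule as the source of protocol-required timing.

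The safeguards are also real. Contraception is required, and women must be reminded of it (Section 5). A woman whose compliance is in doubt should not be entered (Section 3.7). Section 13 allows extra safety assessments case by case. Adverse-event questioning and physical examination at each visit from Day 29 to Day 169 give six chances for a pregnancy to be reported or noticed. These lower the risk, but none is a scheduled test, and the questioning is meant to be non-directive (Section 9.1).

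On size, half the patients receive placebo, so the drug argument applies to the active arm only; the radiation argument applies to both. A pregnancy unnoticed from Day 29 to Day 224 (195 days) is an extreme case. The expected count may be small. As an illustration with assumed inputs, 5 to 19 women followed for 223 days give 5 × 223/365 × 1% = 0.03 to 19 × 223/365 × 1% = 0.12 pregnancies at a 1% annual failure rate, and 0.3 to 1.2 at 10%. The documents give no number of women of child-bearing potential. They state a failure rate (below 1%) only for hormonal or comparable methods, so this range cannot be narrowed.

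**Conclusion.** The concern holds. The schedule row, footnote 4 and Section 8.6.6 agree, and together they leave the treatment period without a required repeat test. The benefit of testing per affected woman runs from one dose plus any scan at that visit, if the pregnancy would soon be noticed anyway, up to five doses and both scan sessions.

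The conclusion rests on the protocol alone. A check in an unseen manual or under local rules would narrow the gap at the sites it covers. Neither the drug's fetal risk nor the number of pregnancies can be estimated here. The primary analysis is not affected. The change should be made because it closes a safety gap at very little cost.

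**What to change.** Amend the row and footnote 4 in Section 8.1 as follows:

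- Add a urine pregnancy test for women of child-bearing potential at Days 29, 57, 85, 113, 141 and 169, using the urine already collected for urinalysis.
- Read the result before dosing, before the Week 12 PET/CT and before the Week 24 CTs.
- If a scan is on a different day from the visit, test on the scan day before the scan. For the PET/CT, do this alongside the same-day finger-prick glucose check and before the tracer is injected.
- After early discontinuation, read the existing EOS test before any CT done at that visit.
- Record all results in the CRF.

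Footnote 12 already puts assessments ahead of study drug, so the order of the visit does not change.

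The cost is one amendment and six strips per woman: seven if the PET/CT is on another day, eight if the Week 24 CTs are as well. Each test takes a few minutes. An occasional false positive will need a serum test. Section 6.6 allows a dose to be held for up to 5 days beyond the ±5-day visit window, so a dose is lost only if the serum result takes longer than the delay allowed.

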## **8.2 Informed consent procedures**

Eligible subjects may only be included in the study after providing written (witnessed, where required by law or regulation), IRB/IEC-approved informed consent. If the subject is capable of doing so, he/she should indicate assent by personally signing and dating the written informed consent document.

Informed consent must be obtained before conducting any study-specific procedures (i.e., all of the procedures described in the protocol). The process of obtaining informed consent should be documented in the subject source documents.

Novartis will provide to investigators in a separate document a proposed informed consent form that complies with the ICH GCP guideline and regulatory requirements and is considered appropriate for this study. Any changes to the proposed consent form suggested by the investigator must be agreed to by Novartis before submission to the IRB/IEC, and a copy of the approved version must be provided to the Novartis monitor after IRB/IEC approval.

Corporate Confidential Information

In the event that Novartis wants to perform testing on the samples that are not described in this protocol, additional Institutional Review Board and/or Ethics Committee approval will be obtained.

## **8.3 Subject screening**

In general, it is permissible to re-screen a subject; however, each case must be discussed and agreed with the Sponsor's medical lead on a case-by-case basis.

Patient re-screening will be allowed in the study in the event of a delay in treatment, e.g., in the event of a washout period of more than 28 days. However, the screening HRCT cannot be repeated and re-screening may not occur if planned dosing will not take place within 8 weeks of these screening imaging assessments.

## **8.4 Subject demographics/other baseline characteristics**

Subject demographic and baseline characteristic data to be collected on all subjects include: date of birth, age, sex, race, predominant ethnicity.

Relevant medical history/current medical conditions data includes data until signature of informed consent. Where possible, diagnoses, and not symptoms, will be recorded.

The following should be recorded on the respective CRF page:

- Relevant medical history/current medical conditions
- Prior and current medications / significant non-drug therapies
- Response to treatment with previous drug therapies (e.g., corticosteroids, methotrexate, azathioprine, TNF- $\alpha$  blockers)

### **8.4.1 Hepatitis screen, HIV screen, tuberculosis screen**

All subjects will be screened for HIV, hepatitis B and C, and tuberculosis. See the Site Operations Manual for details.

### **8.4.2 Alcohol test, drug screen, urine cotinine**

All subjects will be screened for substances of abuse and cotinine. See the Site Operations Manual for details.

## **8.5 Efficacy/Pharmacodynamics**

Pharmacodynamic assessments are specified below, with the methods for assessment and recording specified in the Study Operations Manual. Assessments will be performed/samples collected at the timepoints defined in the [Assessment Schedule](#).

In order to better define the PD profile, the timing of the sample collection may be altered based on emergent data. The number of samples/blood draws and total blood volume collected will not exceed those stated in the protocol.

### **8.5.1 Clinical Outcome Assessments (COAs)**

Corporate Confidential Information

Corporate Confidential Information

Corporate Confidential Information

## 8.5.2 Imaging

Details for HRCT and [F-18]FDG-PET/CT imaging are described in the Parexel Imaging Investigator SOM.

To avoid unnecessary radiation, all screening activities except imaging needs to be completed prior to HRCT scan for eligibility. Evaluation by HRCT for eligibility must be completed prior to the patient undergoing baseline [F-18]FDG-PET/CT. Patients with historical radiologic evidence of parenchymal disease involvement (either HRCT or historical chest x-ray) can be used for eligibility, allowing the HRCT baseline assessment to be performed along with [F-18]FDG-PET/CT on same visit day without waiting for HRCT screening result.

### 8.5.2.1 [F-18] FDG-PET/CT

In this study, [F-18]FDG-PET/CT imaging will provide early evidence for anti-inflammatory effects of IL-1 $\beta$  blockade by ACZ885 on the sarcoidosis process. [F-18]FDG-PET/CT has been shown to detect lung parenchymal involvement at any chest x-ray (CXR) stage, including therapy-resistant disease, and can also provide information on extra-pulmonary disease. Lung fluorodeoxyglucose (FDG) uptake in sarcoidosis has been shown by PET imaging to correlate with important sarcoidosis BAL biomarkers, including percentage neutrophils and CD4:CD8 ratio. In two previous sarcoidosis trials, the [F-18]FDG-PET/CT endpoint was shown to be decreased by 53-55% on treatment (Keijzers et al 2008; Milman et al 2012). Improvements in FVC over a 24 week period have been correlated with decreases in [F-18]FDG-PET/CT compared to baseline, with evidence of improvement by serial [F-18]FDG-PET/CT detected in sarcoid patients reported as early as 1-2 months (Brudin et al 1994; Braun et al 2008; Imperiale et al 2013). Furthermore, [F-18]FDG-PET/CT imaging was able to predict subsequent decreases in FVC and DLco (Sobic-Saranovic et al 2013; Vorselaars et al 2015).

In this study, all patients will undergo whole-body head to mid-thigh [F-18]FDG-PET/CT imaging on a state-of-the-art, 3D PET/CT scanner with a reconstructed resolution of  $\leq$ 5 mm. Subjects with glucose levels above 11 mmol/L (200 mg/dL) should have their scan delayed or be rescheduled as appropriate. The blood glucose level measured prior to the radiotracer administration should be recorded in the image transmittal form (ITF). Subjects will have the radiotracer administered through an i.v. line, whereafter they will be positioned comfortably in a supine position to rest for 60 min, while the radiotracer distributes through the body. Near the end of this 60 min rest, subjects will be asked to void their bladder prior to the scanning procedure. A whole body low-dose attenuation CT will be acquired with a whole body effective dose of 1.5 mSv. Maximum injected radioactivity dose 200 MBq will result in a whole body effective dose of 4 mSv (ICRP 2008). Higher [F-18]FDG activities may be required in large or obese patients to ensure sufficient imaging quality, but it will not exceed 350 MBq. One further imaging scan will be performed at week 12 according to the schedule on enrolled patients with results quantitatively compared to baseline findings using centralized quantitative reading. Detailed information will be provided in the Parexel Imaging Investigator SOM. Total injected activity and body weight will be recorded and used to

compute standardized uptake values. The total dose for all PET/CT scanning (excluding HRCT) in this protocol will be maximally 11 mSv, or 16 mSv in larger or obese patients requiring a higher [F-18]FDG injected dose.

#### **8.5.2.2 Volumetric CT and HRCT**

HRCT will be utilized in this study for assessing therapeutic response at Week 24.

At the time points specified in the schedule, an HRCT scan of the lung without contrast agent will be acquired at full inspiration according to parameters as listed in a separate imaging acquisition manual. In addition to the lung assessment by HRCT, Corporate Confidential Information

Corporate Confidential Information

and require an additional, full

expiratory low-dose CT. Thus, subjects will undergo a total of 2 HRCT scans and two lower dose volumetric CT scans.

With 4 CT scans planned for subjects during this study, the total whole body effective dose per subject from the CT scanning (excluding [F 18]FDG-PET/CT) will be maximally 14 mSv. In all subjects, the baseline and follow-up HRCT scan should be performed where possible on the same scanner, although scans on the PET/CT scanner may be used if they are determined to be comparable with follow-up scans on a different scanner.

